10.1.2 Statistical analysis of the primary endpoint

The Emotional impact score (scale from 0-100) measured every 2^{nd} week will be analysed by a linear mixed model. The model includes a fixed effect of product (standard of care, HeyloTM), a fixed effect of time (2, 4, 6 and 8 weeks), a fixed interaction between product and time, a fixed period effect and a random effect of subject.

The difference between standard of care and $Heylo^{TM}$ at week 8 will be estimated and tested (the primary comparison). Other combinations of differences can be estimated, if relevant.

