10.1.3. Statistical analysis of the secondary endpoint

Participation domain score (scale from 0-100) measured by WHODAS will be analysed by a similar model as the primary endpoint except that the questions are only filled out after 4 and 8 weeks.

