10.1.4. Statistical analysis of the exploratory endpoints

Impact on Usual and social activities score (scale from 0-100) and Impact on Coping ad Control score (scale from 0-100) will be analysed by the same model as for the primary endpoint.

The 3 domain scores based on the WHODAS questionnaires (scale from 0-100) will be analysed by a similar model as the primary endpoint except that the questions are only filled out after 4 and 8 weeks.

Feeling of security evaluated at the end of each test period (5-point Likert scale) will be analysed by a generalized linear mixed model, namely a proportional odds model. The model includes a fixed effect of product (standard of care, $Heylo^{TM}$) and a random subject effect.

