10.1.5. Adjustment for multiplicity

The results from the analyses of the primary and secondary endpoint will be adjusted for multiple testing by a Bonferroni correction to keep a family-wise type 1 error of 5%. The Bonferroni correction for 2 endpoints correspond to evaluate the difference between products as significant if the p-value is less than 0.025. For the analysis of the exploratory endpoints no adjustment for multiple testing will be applied.

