10.2. Sample size

The Emotional impact score (scale from 0-100) will be measured every 2nd week and all measurements will be part of the primary analysis whereas the primary comparison will be evaluated at the end of each test period.

The sample size calculation is based on a simplified model (paired 2-sided t-test). The result of the analysis will be adjusted for multiple testing and therefore a test level of 0.025 will be applied in the sample size calculation. Based on data from the previous CP308 investigation (PP population), it is assumed that the total standard deviation of the primary endpoint is 20.6 and that the total variation 20.6² is divided so that the residual variation is 14.4².

Based on the above assumptions 108 subjects should answer the questionnaires at the end of each test period to ensure a power of 81%, if the true difference between the two treatments (with and without HeyloTM) is 6 (minimal important difference is in the range of 5-10 according to the validation of the OLI score) [7]. To take a potential drop-out (25%) into account it is recommended to include 144 subjects.

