10.3. Level of significance and power

A two-sided significance level of 5% will be applied. For a description of the power see section 10.2 above.

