10.4. Pass/fail criteria

The purpose of the investigation is fulfilled if a statistically significant improved mean difference in the primary or secondary endpoint is obtained with the test product compared to Standard of Care.

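### The mixed model's only covariance term is a random subject effect; if a subject's scores are more alike within a period than across periods, the week-8 test at 0.025 rejects too often

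*Combined protocol and SAP*

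**What the plan says.** Section 10.1.2 specifies a linear mixed model for the scores at weeks 2, 4, 6 and 8. Its fixed effects are product and time, with "a fixed interaction between product and time, a fixed period effect and a random effect of subject". The primary comparison is the product difference at week 8. Section 10.2 confirms that "all measurements will be part of the primary analysis whereas the primary comparison will be evaluated at the end of each test period".

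The model is then reused. The WHODAS participation score "will be analysed by a similar model as the primary endpoint except that the questions are only filled out after 4 and 8 weeks" (10.1.3). The other OLI scores are covered by "will be analysed by the same model as for the primary endpoint" (10.1.4), and that section gives the exploratory WHODAS domain scores a similar model.

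On error control, 10.1.5 applies a Bonferroni correction "to keep a family-wise type 1 error of 5" per cent, so each endpoint is tested at 0.025, and 10.3 makes testing two-sided. Under 10.4 the trial succeeds if "a statistically significant improved mean difference in the primary or secondary endpoint is obtained with the test product".

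Section 10 names no subject-by-period effect, residual covariance structure, robust standard error or degrees-of-freedom method.

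**The concern.** The product comparison is made between a subject's two periods. Whatever shifts all of a subject's scores in one period relative to the other goes straight into the week-8 difference. Examples are an individual response to the device, a change of stoma product during a period (which 5.3 records), or a good or bad spell that outlasts two weeks. Repeating the questionnaire within the period does not average it out.

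A lone random subject effect has no place for this variation. It goes into the residual, which is pooled over all eight scores, most of whose information concerns week-to-week noise within a period. The residual is then too small for the week-8 contrast.

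The p-values and confidence intervals for both confirmatory endpoints are at stake, and with them the family-wise error that 10.1.5 promises. The point estimate, the data collected and the 144 subjects are not affected.

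**Working it through.** **Inputs.** From 10.2: total SD 20.6, residual SD 14.4, 108 completers, true difference 6, test level 0.025, drop-out 25%. From 10.1.2 and 10.1.3: T = 4 scores per period (OLI) and T = 2 (WHODAS). Assumed: the share s of the within-subject variance 14.4² that is subject-by-period variation. The documents do not give it, so a range is shown.

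**The plan's own figure.** The SE of the week-8 difference is 14.4 × √(2/108) = 1.96. Then 6/1.96 − 2.241 = 0.82, a power of 79.4% by normal approximation (78.4% by exact paired t), against the stated 81%. 108/0.75 = 144. The sizing is reproduced to within about 2 to 3 points. The paired t-test used there takes its error from the observed differences, so it does not depend on the assumption examined here.

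**Implied correlation.** 1 − 14.4²/20.6² = 0.511 for every pair of scores from one subject, within or across periods.

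**What the model estimates.** Write the within-subject variance as s_e² (occasion) + s_sp² (subject-by-period). Each subject has 2T − 1 within-subject degrees of freedom. One of them, the difference between period means, has mean square s_e² + T·s_sp². The other 2T − 2 have s_e². The pooled residual therefore has expectation

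s_e² + [T/(2T − 1)]·s_sp²,

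whereas the week-8 contrast needs s_e² + s_sp². With equal week variances,

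- SE ratio (model/true) = √[(1 − s) + s·T/(2T − 1)]
- two-sided error = 2·[1 − Φ(2.2414 × ratio)]

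| Share s | Ratio, T=4 | Error, primary | Ratio, T=2 | Error, secondary | Sum of the two | Half (improvement only) |
|---|---|---|---|---|---|---|
| 0% | 1 | 0.025 | 1 | 0.025 | 5.0% | 2.5% |
| 10% | 0.978 | 0.028 | 0.983 | 0.028 | 5.6% | 2.8% |
| 25% | 0.945 | 0.034 | 0.957 | 0.032 | 6.6% | 3.3% |
| 50% | 0.886 | 0.047 | 0.913 | 0.041 | 8.8% | 4.4% |
| 75% | 0.824 | 0.065 | 0.866 | 0.052 | 11.7% | 5.9% |

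The sum is the Bonferroni upper bound with the same share on both endpoints. At s = 50% the model SE is 1.96 × 0.886 = 1.74 against a true 1.96.

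**Simulation of the planned model** (108 subjects, two sequences, 12,000 replicates, same five shares):

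- T = 4: 0.024, 0.030, 0.035, 0.047, 0.063
- T = 2: 0.025, 0.029, 0.032, 0.044, 0.053

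**Serial correlation instead of a constant period shift.** With AR(1) within period and correlation 0.3, 0.6 or 0.8 between successive scores, the simulated primary error is 0.034, 0.047 or 0.061.

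**Unequal week variances.** At a 25% share the planned model gives 0.022 if the week-8 SD is 10% below the other weeks and 0.056 if it is 15% above. The inflation disappears when the week-8 SD is about 7% lower (25% share) or 14% lower (50% share).

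**With a subject-by-period effect added** (20,000 replicates, Satterthwaite degrees of freedom, same five shares):

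- T = 4: 0.026, 0.026, 0.025, 0.023, 0.025
- T = 2: 0.024, 0.026, 0.026, 0.025, 0.027

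**The case against.** The strongest reply is that the decisive input is missing. Section 10.2 gives only a total and a residual SD, so the documents cannot show that the test will misbehave; at a zero share it does not. That stands, and it makes the finding conditional. It does not justify a model that is valid only at a zero share.

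The direction also depends on the week variances: a sufficiently smaller week-8 SD cancels the inflation or makes the test conservative. That stands too, but a larger week-8 SD makes it worse, and the plan offers no reason to expect either.

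An individual response to the device is a weak mechanism under a strict null in which the device affects nobody, since that component is then zero. This is correct. Serial correlation and period-specific drift do not need a device effect, however, and the AR(1) results show inflation of the same size.

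Section 10.1.2 lists the effects in the model and does not mention the residual structure, so a within-period structure could be added without contradicting it. That is possible, but the natural reading of the text is independent residuals, and nothing else in section 10 suggests otherwise.

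Finally, 10.4 counts only improvement. On that basis the bound on false success passes 5% only at a share of about 61%, and positive correlation between the endpoints would lower it. This is fair and limits the practical harm. The two-sided level set in 10.1.5 and 10.3 is still exceeded at any positive share when week variances are equal, and the confidence intervals are too narrow whichever way success is counted.

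**Conclusion.** The concern holds, conditionally. As written, the model assumes equal correlation within and across periods. Any positive subject-by-period variance, with week variances roughly equal, makes the week-8 test anti-conservative. For an assumed share of 25 to 50%, the primary test runs at 0.034 to 0.047 and the secondary at 0.032 to 0.041 instead of 0.025, and the family-wise bound is 6.6 to 8.8% instead of 5%. At a zero share nothing is wrong.

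The share is an assumption throughout, so confidence in the size is medium; the mechanism itself is not in doubt. It should be fixed before the analysis. For the exploratory endpoints in 10.1.4, which carry no multiplicity control, the consequence is limited to confidence intervals and nominal p-values.

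**What to change.** In 10.1.2, specify two random effects, subject and subject-by-period, and name Kenward-Roger degrees of freedom. Make the same change in 10.1.3 and in the linear models of 10.1.4. In SAS this is one more RANDOM statement and a change of wording, with no new data, visits or subjects. At a zero share the added component is estimated near zero and the simulated error is 0.026.

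The added term still assumes equal week variances. In simulation it gave 0.041 to 0.042 with a week-8 SD 15% higher and 0.014 to 0.016 with one 10% lower. An unstructured residual covariance over weeks 2, 4, 6 and 8 within period would allow unequal variances. If that is chosen, the text must say that the random subject effect is kept. Without it the SE becomes 20.6 × √(2/108) = 2.80 instead of 1.96, and power for 6 points falls from about 79% to 46% (6/2.80 − 2.241 = −0.10).

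The paired week-8 contrast with period adjustment would be a useful prespecified sensitivity analysis. It stayed at 0.024 to 0.027 in every simulated case, including unequal week variances, but it uses only subjects with both week-8 scores.

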10.1.3. Statistical analysis of the secondary endpoint

Participation domain score (scale from 0-100) measured by WHODAS will be analysed by a similar model as the primary endpoint except that the questions are only filled out after 4 and 8 weeks.

10.1.4. Statistical analysis of the exploratory endpoints

Impact on Usual and social activities score (scale from 0-100) and Impact on Coping ad Control score (scale from 0-100) will be analysed by the same model as for the primary endpoint.

The 3 domain scores based on the WHODAS questionnaires (scale from 0-100) will be analysed by a similar model as the primary endpoint except that the questions are only filled out after 4 and 8 weeks.

Feeling of security evaluated at the end of each test period (5-point Likert scale) will be analysed by a generalized linear mixed model, namely a proportional odds model. The model includes a fixed effect of product (standard of care, $Heylo^{TM}$) and a random subject effect.

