V3 will also be the termination visit unless a situation occurs where a subject terminates earlier than expected. If this is the case the subject will as the last visit have the termination visit performed.

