5.7. Randomization procedure

All subjects that meet the inclusion and exclusion criteria will be randomized into one of two treatment sequences at V1, with a cross-over after 8 weeks (Visit 2). Subjects with stoma surgery less than 3 months, will be stratified according to time since surgery.

Treatment sequences:

Sequence A: Heylo™ + Standard of Care cross-over to Standard of Care

Sequence B: Standard of Care cross-over to Heylo™ + Standard of Care

When testing the Heylo™ it must be done together with subject's usual ostomy product and in the Standard of Care period subjects will only use their own product.

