- Insurance of subject's wellbeing and follow-up on subject's compliance with study specific procedures (e.g., completing questionnaires and use of Investigational device + Standard of Care OR Standard of Care only)
- Subject completing todays questionnaires:
 - Emotional Impact (OLI)
 - Coping and in control (OLI)
 - Usual and Social activities (OLI)
 - WHODAS 2.0:
 - Understanding and communicating
 - Getting around
 - Self-care
 - Getting along with people
 - Life activities
 - Participation in society
 - Feeling of security, see section 5.3 and Appendix 4

- Assessment of:
 - Leakage outside baseplate, see section 5.3 and Appendix 4
 - Change in current stoma product, see section 5.3 and Appendix 4
 - o Change in Heylo size, if relevant, see section 5.3 and Appendix 4
 - o Review of AEs, ADEs, SAEs, SADEs, Device deficiencies and protocol deviations
- Collect unused Heylo™ devices from subject who have tested this in the last 8 weeks
- Collect used Heylo[™] devices (only charger and transmitter), from subjects who have tested these in the last 8 weeks
- Termination and completion of the study

Follow-up call - Performed 7 days ±2 days after visit 1 and visit 2:

- Ensure compliance with the provided product and study procedures
- Insurance of subject's wellbeing.

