10.1.1. Definition of analysis populations

Intention to Treat (ITT) and Safety populations will be defined at a formal data review meeting before database lock. As a minimum, the data manager, the clinical manager, and the statistician will be involved in the classification of subjects.

The ITT population (full analysis set) will be constituted by all randomised subjects with valid informed consent who have been exposed to at least one product, with information on at least one endpoint.

The Safety population will constitute by subjects who have given informed consent.

All statistical analysis will be based upon the ITT population whereas adverse events and device deficiencies will be assessed based on the safety population. Invalid individual data points may be omitted from analysis even though the corresponding subject is part of the ITT population. Any exclusion of data points will be documented.

A formal per protocol (PP) population is not planned due to the explorative nature of the investigation. Considering the data obtained it might be considered to make additional explorative analyses based on a subset of the ITT population.

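### Exploratory analyses only, low priority: the Feeling of security model in 10.1.4 has no period effect, and its three WHODAS domains do not match the five declared in 5.3

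*Combined protocol and SAP*

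**What the plan says.** **Design.** Section 5.7: "All subjects that meet the inclusion and exclusion criteria will be randomized into one of two treatment sequences at V1". Sequence A takes Heylo first and sequence B standard of care first, with the switch at week 8. No allocation ratio is given.

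**Models.** The primary model in 10.1.2 contains product, time, "a fixed interaction between product and time, a fixed period effect and a random effect of subject". Section 10.1.3 carries this over: "Participation domain score (scale from 0-100) measured by WHODAS will be analysed by a similar model as the primary endpoint". Section 10.1.4 uses the same model for the two remaining OLI scores and a similar one for the WHODAS domains. Feeling of security alone has its model written out separately: "The model includes a fixed effect of product (standard of care, $Heylo^{TM}$) and a random subject effect".

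**WHODAS domains.** Section 10.1.4: "The 3 domain scores based on the WHODAS questionnaires (scale from 0-100) will be analysed by a similar model". The three are not named. Section 5.3 and the synopsis each list five exploratory domains: understanding and communicating, getting around, self-care, getting along with people, and life activities. Section 7.1 collects all five at V1, V2 and V3 and every fourth week.

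**Who is analysed.** The ITT set in 10.1.1 keeps randomised subjects "exposed to at least one product, with information on at least one endpoint", so a subject with a period-1 answer only still contributes.

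**The concern.** **Period effect.** Each subject gives one security answer at the end of period 1 and one at the end of period 2. Dropping the time term is natural, because 10.1.4 analyses only the end-of-period answer. That does not justify dropping period. If answers drift between periods, through habituation, stoma maturation or simply being in a trial, the drift enters the product contrast with opposite signs in the two sequences. It cancels only if the sequences contribute equally. Even then, on the logit scale, the estimate is slightly attenuated.

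**Domain count.** With three unnamed domains against five declared, two exploratory endpoints have only the descriptive summaries of 10.1. Exploratory endpoints carry no multiplicity adjustment (10.1.5), so leaving the subset unnamed means the choice of what to model could be made after the data are seen.

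**Working it through.** **1. Period effect: inputs**

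- From the plan: 144 randomised, 25% drop-out and 108 completers (10.2: 108 / 0.75 = 144); a five-category answer; two sequences.
- Assumed, because the plan gives no values: 72/72 allocation; product log odds ratio β = 0.60; period log odds ratio π = 0.25, 0.5 or 1.0; subject SD 1.5; cut-points −2.5, −1, 0.5, 2; and the share of the 36 dropouts who answer in period 1, from none to all.

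**2. Method**

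The model is logit P(Y ≤ k) = c_k − (β·Heylo + π·period 2 + u), with u ~ N(0, 1.5²). Exact cell probabilities come from 40-point Gauss-Hermite quadrature. The expected log-likelihood is maximised with and without π, and standard errors come from its Hessian. Dropouts who answer add their period-1 marginal likelihood.

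**3. Results with period left out (true β = 0.600)**

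Ranges cover no dropout to every dropout answering in period 1.

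| Completers A/B | π = 0.25 | π = 0.5 | π = 1.0 |
|---|---|---|---|
| 54/54 | 0.597 | 0.587 | 0.551 |
| 57/51 | 0.583–0.587 | 0.559–0.568 | 0.499–0.517 |
| 51/57 | 0.606–0.610 | 0.605–0.614 | 0.585–0.602 |
| 60/48 | 0.569–0.578 | 0.532–0.550 | 0.447–0.483 |
| 48/60 | 0.616–0.624 | 0.624–0.641 | 0.619–0.655 |

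With period in the model the estimate is 0.600 in every cell.

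**4. Size in standard errors**

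- 54/54: (0.600 − 0.587) / 0.262 = 0.05 at π = 0.5; (0.600 − 0.551) / 0.261 = 0.19 at π = 1.0.
- 60/48 at π = 0.5: (0.600 − 0.550) / 0.249 = 0.20 to (0.600 − 0.532) / 0.261 = 0.26.
- 60/48 at π = 1.0: (0.600 − 0.483) / 0.246 = 0.48 to (0.600 − 0.447) / 0.259 = 0.59.
- Standard error without period 0.25 to 0.26, with period 0.25 to 0.27. Leaving period out does not inflate it.

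**5. Hand check on the imbalance part**

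The within-subject contrast is β − π in sequence A and β + π in B, so imbalance among completers shifts the estimate by about −π(nA − nB)/(nA + nB). For 60/48 and π = 0.5 this is −0.5 × 12/108 = −0.056. Added to the balanced value, 0.587 − 0.056 = 0.531, against 0.532 in the table.

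**6. No product effect**

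Balanced sequences give no bias. With 60/48 the estimate is −0.037 to −0.055 at π = 0.5 and −0.068 to −0.104 at π = 1.0.

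**7. How likely is the imbalance?**

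If 36 dropouts fall at random on 72/72, the number of completers in sequence A is hypergeometric with SD 2.6. A split of 57/51 or worse, in either direction, has probability 0.336 (about 0.17 each way). For 60/48 or worse it is 0.033.

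**8. Sensitivity**

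With all dropouts answering, changing the subject SD to 1.0 or 2.0, or skewing the cut-points, leaves 60/48 at 0.546–0.554 (π = 0.5) and 0.477–0.491 (π = 1.0). A simpler matched-pair logit on a binary split shows the same pattern: a true 0.70 becomes 0.683 at π = 0.5 with a 50:50 split and 0.586 with 60:40.

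**9. Domain count**

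Declared exploratory WHODAS domains in 5.3 and the synopsis: 5. Modelled in 10.1.4: 3. Not modelled: 5 − 3 = 2, unnamed. Adding participation makes six, and 10.1.3 already handles it.

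**The case against.** Both points are small. The plan says nothing about the size of a period effect, so every magnitude above is illustrative. With balanced sequences the shift is 0.05 standard errors at π = 0.5 and zero under the null. A 60/48 split has only a 3.3% chance under random dropout, and with 51/57 at π = 1.0 the attenuation and the imbalance shift nearly cancel. All of this stands, and it is why the priority is low.

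The 36 lost pairs are also an upper case. For a subject who stops early, 5.1 says: "If this is the case the subject will as the last visit have the termination visit performed". The V3 list in 7.1, headed as the termination visit, includes "Feeling of security, see section 5.3 and Appendix 4". A subject leaving during period 2 may therefore supply both answers. If every dropout did, the data would return to 72/72, with 0.587 or 0.551: the imbalance shift goes and the attenuation stays. Early answers do not help if the randomised numbers themselves are unequal. With 76/68 randomised and 25% lost in each sequence (57/51), the estimate is 0.559–0.560 at π = 0.5 whether or not dropouts answer.

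On the domain count, the endpoint rationale in 5.4 mentions participation, getting along with people, and life activities, which makes three WHODAS domains. That may be where the number comes from, so calling it a miscount is only a guess. It does not settle the matter, because one of those three is the secondary endpoint with its own section. It is also fair to say that the sponsor could choose to model fewer than five and leave the rest descriptive, but 10.1.4 would then have to name them.

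**Conclusion.** Both points hold. The omission of period from the Feeling of security model is unexplained and inconsistent with every other modelled score in the plan. If there is a period effect, the consequence is a slight attenuation with equal sequences and a shift in either direction with unequal ones. In the illustration this ranges from 0.05 standard errors (54/54, π = 0.5) to 0.59 (60/48, π = 1.0). A negative period effect, or imbalance the other way, reverses the sign of the imbalance shift. These sizes rest on the assumed product and period effects, subject SD, cut-points and allocation; the direction of the argument does not.

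The count of three against five is a plain contradiction that needs no assumption.

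Only exploratory endpoints are affected. The success rule (10.4), sample size (10.2) and Bonferroni correction (10.1.5) do not depend on either point, so this is a low-priority correction worth making because it is nearly free.

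**What to change.** In 10.1.4:

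- Add a fixed period effect to the proportional odds model for Feeling of security.
- Replace the reference to three WHODAS domain scores with the five declared in 5.3 by name: understanding and communicating, getting around, self-care, getting along with people, life activities.

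The cost is one degree of freedom in one exploratory model, with a rise in standard error of at most about 0.01, and one corrected list. Period follows from sequence and visit, and all five domains are already collected, so no data, visits or subjects are added.
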